Our rationale for this research is that study results, if found to be successful, will provide an evidence-based framework to undertake a large-scale randomized control trial (RCT) to improve long-term health outcomes for individuals with a mobility disability.

The primary study endpoints are the feasibility and effectiveness of the adapted intervention as measured by outcomes listed in Aims 1-3. The primary safety endpoints include no increased risk of secondary health conditions that are related to participants' primary disability.

The risks posed to study subjects (discomfort associated with blood draws, injury while engaging in physical activity, psychological stress associated with behavior change) are minimal, while the intervention poses multiple substantial benefits to the study participants in terms of health, chronic disease risk, skill-building, and quality of life. The research poses potentially great benefits to society, as individuals with impaired mobility experience a higher prevalence of obesity(1) and greater burden of obesity-related chronic conditions,(1, 2) including a four times higher rate of diabetes.

2. Background: Despite striking weight-related heath disparities, people with mobility impairments remain underserved by public health efforts to address weight loss(3) and effective lifestyle

interventions are lacking.(3-7) People with mobility impairments are also less physically active(8) than those without disability and report being less likely to receive exercise counseling.(9) Additionally, the adverse effects of obesity for those with mobility impairments may be greater than in the general population as excess weight and additional health problems may further restrict people's functioning and independence.(3) The tenets of weight loss to eat less and exercise more are equally relevant for people with mobility impairments; however, approaches to deliver the message and facilitate adherence must be tailored to address the unique physical, environmental, and attitudinal barriers associated with mobility impairment.

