Safety measures will include assessment of participants' 1) albumin levels, to assure adequate protein intake, 2) upper arm circumference, to assure preservation of lean muscle mass, and 3) weekly reporting of health events and pressure sores in particular.

4. Study Procedures:

Phase 1. Board members will address the content, layout, format, language, behavior change strategies, and delivery approaches for adapting the GLB program for a mobility impaired sample. To facilitate building rapport, the first board meeting will be convened in person (Dallas, TX). The full-day meeting will allow members to critically review and discuss the existing program and materials and offer recommendations for specific adaptations. GLB materials will be mailed in advance to assure everyone has sufficient time to review information before the meeting. Changes recommended during initial meetings will be fully reviewed and discussed during subsequent teleconferences. The board will convene multiple times per year during the 3 year study, with meetings scheduled 3 times in year 1, 2 times in year 2, and 4 times in year 3 as the team analyzes results and plans next steps.

Phase 2.

The PI and the program coordinator will perform testing and deliver the intervention with the assistance of a trained research assistant. The PI has conducted exercise interventions for people with disabilities for 15 years and is knowledgeable about different types of disabilities (e.g., spinal cord injury, MS, cerebral palsy) and exercises that are appropriate to do within the context of the specific impairments and limitations. The program coordinator is a graduate student at the UT School of Public Health who has completed the University of Pittsburgh Diabetes Prevention Support Center training to deliver the GLB. She assisted with delivery and testing of a pilot modification of the GLB for impaired mobility in 2014. The research assistant will be hired from one of the graduate programs at UT Southwestern, either Health Promotion/Behavioral Sciences in Public Health, Psychology, Physical Therapy, or Vocational Rehabilitation. The PI will supervise all study staff.

It is anticipated that intervention group participants will be involved for 12 months and wait-list control group participants for 18 months.

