Individuals with impaired mobility are at elevated risk for myriad conditions, such as chronic pain, spasticity, fractures, fatigue, depression, bowel and bladder problems (including urinary tract infections and kidney stones), and pressure sores. We expect any of these conditions to occur during the course of the study but do not anticipate that they will be related to the study. There is no published evidence to suggest that intentional weight loss poses an increased risk for these health problems above their existing risk. Nevertheless, given the dearth of weight loss research in this population, multiple safety measures (as described in 11 below) will be implemented. As research suggests that *unintentional* weight loss can increase the risk of pressure sores in the elderly, and as pressure sores are a common but potentially serious complication among people of all ages with mobility impairments, particular attention will be paid to the prevention and reporting of pressure sores.

Risks to being active include minor musculoskeletal pain and injuries (e.g., soreness, bruising) and cardiovascular events, generally seen in people with underlying disease. Minor discomforts and injuries such as soreness are likely for those who have not previously been exercising. Injury is less likely for those who have been exercising and progress at the recommended level. Risks and discomforts associated with increased fiber and fluid intake may include increased gas, bloating, and potential changes to the timing of bowel and bladder programs that participants should consider. Participants may experience psychological stress associated with health behavior change.

11. Subject Safety and Data Monitoring:

The procedures in place to assure appropriate precautions for safety include the following.

Eligibility and intervention.

- Participants are only eligible to participate in the intervention once their primary care physician provides signed approval that they have no contraindications to initiating a program of moderate intensity exercise and dietary change to promote weight loss.

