- 9) In addition, study staff will use text messages and/or email to send scheduled messages throughout the course of the study, asking participants to report whether any adverse event has occurred. If a participant answers yes, study staff will follow up by phone or encrypted email to ascertain the details of the event. Staff will then follow up with the participant regularly until the issue has been resolved. Participants will be informed that they may be responsible for charges incurred for text messaging.
- 10) Albumin levels collected at baseline 3 months, 6 months, and 12 months will be assessed for adequate nutrition, and participants at risk for malnutrition will be encouraged to see their doctor and discontinue calorie restriction.
- 11) Finally, we will give all participants a phone number that provides direct access to the PI 24-hours a day.

12. Procedures to Maintain Confidentiality:

In order to assure participant confidentiality, all participants will be assigned a unique study identification number. Only one master list will be maintained by the PI on a secure network drive in a password protected file. All databases will use the subject ID number rather than names. Signed consent forms will be maintained by the PI behind a locked door in a locked file cabinet separate from the linked file and hard copies of data files. Investigators at the University of Pittsburgh, Baylor Institute for Rehabilitation and Texas Tech University will access the data via a secured shared drive or encrypted flash drive and their respective IRBs' approval to do so will be obtained.

All bloodwork will be conducted by UTSouthwestern labs and collected, analyzed, and disposed of according to the UTSW lab protocols. De-identified blood values for the specified biomarkers only will be communicated to the study staff. The study staff will not store or maintain any specimens.

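### The adverse-event message in Section 11 does not carry through the weekly, pressure-sore-specific reporting listed in Section 3, and the other expected conditions have no named event query after baseline

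*Combined protocol and SAP*

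**What the plan says.** Section 1 (Introduction and Purpose) defines the primary safety endpoints as including "no increased risk of secondary health conditions that are related to participants' primary disability". It names no conditions.

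Section 3 (Concise Summary of Project, Safety measures) lists three safety measures. The third is "weekly reporting of health events and pressure sores in particular".

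Section 10 (Potential Risks) gives the conditions for which this population is at raised risk, as examples: "chronic pain, spasticity, fractures, fatigue, depression, bowel and bladder problems (including urinary tract infections and kidney stones), and pressure sores". It continues: "We expect any of these conditions to occur during the course of the study", and adds that they are not anticipated to be study-related. It also states that "particular attention will be paid to the prevention and reporting of pressure sores", and refers forward to Section 11 for the safety measures.

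Section 11 (Nutrition and adverse event monitoring) has two participant-reporting items. Item 8 encourages participants to report events when they happen. Item 9 provides scheduled text or email messages "asking participants to report whether any adverse event has occurred". It then says: "If a participant answers yes, study staff will follow up by phone or encrypted email to ascertain the details of the event". No interval is stated and no condition is named.

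Section 4 (Visits) puts the survey of past common health complications among the procedures done once, at baseline. Section 14 (Biostatistics) plans models for the effectiveness outcomes and describes no safety comparison.

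**The concern.** The endpoint asks whether a set of familiar, recurring problems becomes more frequent during the programme. The operative query asks whether an adverse event has happened, and details are sought only after a yes. Someone who has lived for years with bladder infections, pain or skin breakdown must decide alone whether the latest episode qualifies. Different people will decide differently, and the two arms may do so too.

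Safety is claimed here by not finding an increase, so the quality of event capture bears directly on the conclusion. If capture is poor or uneven, neither an apparent absence of excess nor an apparent excess can be read with confidence. Section 10 itself cites the scarcity of weight-loss research in this population as the reason for extra safety measures.

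**Working it through.** The plan has no figure to reproduce: it gives no event rate, reporting sensitivity, safety margin or safety test. The check is a reading of the text, followed by an illustration on assumed values.

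**Text**

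1. *Governing section.* Section 10 sends the reader to Section 11 for the safety measures, so the reporting procedure should be found there.
2. *Interval.* Section 3 says weekly. Item 9 says scheduled, throughout the study, without an interval.
3. *Content.* Section 3 singles out pressure sores. Item 9 does not name them. Elsewhere in Section 11 they appear under nutrition, under preventive instruction and as an example of when to see a doctor. None of these asks whether one has occurred.
4. *Other conditions.* The remaining Section 10 conditions are named in no event query in Section 3 or Section 11, and the one survey on health complications is not repeated after baseline.
5. *Endpoint.* Section 1 gives a category and Section 10 gives examples. Neither the endpoint nor the query fixes which conditions count.

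**Illustration**

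Input from the documents: n = 32 per group (Section 14, Sample size and power).

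Assumed: true 6-month risks p0 (control) and p1 (intervention); reporting sensitivities s0 and s1; no false reports.

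- Observed risk = s × p
- Expected participants with a reported event = 32 × s × p
- Observed risk difference = s1·p1 − s0·p0; observed risk ratio = (s1·p1)/(s0·p0)
- Power (two-sided 5%, normal approximation), with a and b the observed risks and m their mean: Φ{[(b − a) − 1.96·√(2m(1 − m)/32)] / √([a(1 − a) + b(1 − b)]/32)}

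| True risk, control / intervention | s0 / s1 | Observed risk, control / intervention | Difference (points) | Ratio | Power |
|---|---|---|---|---|---|
| 20% / 40% | 1.0 / 1.0 | 20% / 40% | 20 | 2.0 | 41% |
| 20% / 40% | 0.8 / 0.8 | 16% / 32% | 16 | 2.0 | 32% |
| 20% / 40% | 0.5 / 0.5 | 10% / 20% | 10 | 2.0 | 20% |
| 20% / 40% | 0.3 / 0.3 | 6% / 12% | 6 | 2.0 | 13% |
| 20% / 40% | 0.5 / 0.8 | 10% / 32% | 22 | 3.2 | 58% |
| 20% / 20% | 0.5 / 0.8 | 10% / 16% | 6 | 1.6 | – |
| 30% / 30% | 0.5 / 0.8 | 15% / 24% | 9 | 1.6 | – |

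Example, third row: 32 × 0.5 × 0.20 = 3.2 and 32 × 0.5 × 0.40 = 6.4 participants with a reported event, against 6.4 and 12.8 with full capture.

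Other assumed risks behave in the same way. At s = 0.5 in both arms, power falls from 52% to 26% for 10% vs 30%, and from 37% to 17% for 30% vs 50%.

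Equal under-reporting shrinks the difference and leaves the ratio unchanged. Better capture in the intervention arm can create an excess where none exists.

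**The case against.** **Sections 3 and 11 can be read together.** Section 3 may supply the interval and focus, and item 9 the channel. Item 9 describes a message without giving its wording, so the message as sent may name pressure sores. This stands in part: the documents do not show that it will omit them. But a reader following Section 11 alone would not know to include them or to send the message weekly. This reading also does nothing for the other conditions.

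**Other contacts touch these conditions.** At every visit staff ask about medications that may influence weight, with drugs for pain and depression among the examples, and a quality-of-life questionnaire is repeated. Spontaneous reporting is encouraged. So it would be wrong to say that nothing else bears on these conditions after baseline. None of these contacts, however, is described as recording whether a named event occurred.

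**A generic yes/no may be deliberate.** Section 4 (Communication) asks participants not to send sensitive health information by text. A checklist answered by text would conflict with that. This stands and shapes the fix.

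**Wording is not the main limit.** Even with perfect capture, power for the assumed doubling is about 41%, and Section 14 plans no safety test. This also stands, and it keeps the point modest.

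A reader might infer that events will be under-reported and the result pushed towards no increase. The documents do not support that. They give no sensitivity, and how participants are told to understand an adverse event may be explained in consent material not reviewed here. The one-way direction also needs equal capture in both arms. Intervention participants have group sessions and are offered monthly coach calls, whereas waiting controls are described as receiving mailed newsletters, so capture may well be unequal.

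**Conclusion.** The point holds as a gap between what Section 3 promises and what Section 11 specifies, and as the absence of a named event query after baseline for the other Section 10 conditions. It makes the primary safety endpoint hard to interpret, because participants decide what counts and may do so differently by arm.

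It does not establish that events will be missed, how many, or in which direction the comparison would be biased. On the assumed values, a 20-point difference could appear as anything from 6 to 16 points with equal sensitivity of 0.3 to 0.8. It could appear as 22 points with sensitivity 0.5 in control and 0.8 in intervention, and a spurious 6 to 9 points could arise under no true difference. These figures rest entirely on assumed risks and sensitivities.

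Nor should it be said that the endpoint consists of named conditions: Section 1 names none. This is a worthwhile, inexpensive improvement to ascertainment rather than evidence of a biased result.

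**What to change.** 1. **Reconcile item 9 of Section 11 with Section 3.** State that the message goes out weekly, with identical wording and timing in both arms, and name pressure sores and the other Section 10 conditions in the question. Keep one yes/no reply, with details taken by phone or encrypted email as item 9 already provides, so that the text-message rule in Section 4 is respected.
2. **Repeat the baseline question on common health complications** at the 3- and 6-month visits in both arms, asking about the period since the last visit. Check that it covers the Section 10 list, since its wording is not in the documents. Use these answers for the between-arm safety summary, and say in Section 14 that this summary will be reported.

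Cost: a slightly longer message, one extra survey page at visits already scheduled for both groups, and higher reported event counts, which should be expected when the results are read. No treatment or clinical rule changes.

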 - 2) Invited to participate in teleconference-based group meetings, delivered in accordance with the GLB schedule and led by a trained lifestyle coach; meetings will be offered via a videoconferencing technology, such as Adobe Connect, which allows people to connect by landline, cell phone, tablet, or computer and connect either via audio alone or audio and video.
 - **3)** Invited to an optional in person meeting each month, during which participants can be weighed;
 - 4) Offered monthly individualized phone support from a lifestyle coach;
 - 5) Invited to include caretakers or key family support in meetings, if desired
 - **6)** Offered exercise aids that are appropriate for individuals with impaired mobility, including disability appropriate exercise DVDs, Garmin vivofit arm-based exercise trackers with heart rate monitors, pedal exercisers, and therabands (versus the GLB's offering of nonmodified exercise DVDs, pedometers, and other incentives). Participants will also be given Calorie

King™ calorie counting books, measuring cups, and a scale, in accordance with the mainstream GLB.

Conditions that may result in the subject exiting the study before the expected completion date include subject withdrawal of consent or decision not to continue their participation. Because of the remote nature of the intervention, participants may choose to continue the study despite adverse health events including hospitalization. However, participants will be explicitly advised to follow their doctors orders in all matters, including those most relevant to the study—physical activity and diet.

Outcome measures.

Feasibility measures will assess participants' adherence with key intervention components: **1)** group meeting attendance, **2)** individualized phone call attendance, and **3)** for the first 12 weeks only, self-monitoring of food intake and PA.

Effectiveness measures. **Primary outcomes** to assess the GLB effects will be collected at baseline and again at 3, 6, and 12 months. These will include participant's weight, PA, self-efficacy, function, and QOL. **Secondary outcomes** will be measured at baseline, 6, and 12 months and will include waist circumference, BP, A1c, serum lipids.

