Baseline, 6 months, and 12 months:

- 1) Study staff will measure participants' blood pressure using an automatic cuff (Omron 7 Series wrist blood pressure monitor); upper arm circumference, and waist circumference measured at the umbilicus, with participants in a supine position when possible. Participants who have higher level injuries and/or difficulties in lying down will be measured in a seated position, or if they choose, transferred to the mat using a Hoyer lift.(34) Patients who do not require a Hoyer lift but who do require assistance in transferring from their chair will to a mat table can choose to be assisted by study staff, who have been trained by physical therapists in performing transfer assists.
- 2) A phlebotomist will draw participants' blood via venipuncture, and a UTSW lab will measure serum lipids to assess cardiovascular disease risk, A1c to assess participants' average blood sugar level over the past 2-3 months, and albumin to assess blood protein levels and nutritional status. The total volume of blood drawn will be 10mL, collected in 2 vials of 4-5 mL each.

Baseline and final visit (12 months for experimental group, 18 months for control):

 In addition to the above, participants will be asked to answer paper/pencil survey questions to assess the following: functional abilities in activities of daily living and instrumental activities of daily living (using the LIFE-H short form questionnaire);

- functional abilities around diet, eating, and fitness (using portions of the LIFE-H long form); and types of physical activities (using the 1-year MAQ).
- 2) Structured interviews with participants, conducted either in person or by phone, will gather qualitative information on topics such as motivation for joining the program; past weight loss experiences; who selects, purchases, and prepares food in the home; changes in these roles over time; the process of lifestyle change and its effects on sense of self and relationships; and barriers and facilitators to change. Similar questions may be asked and responses gathered during one or more of the monthly individualized phone support calls throughout the course of the program. Interviews may be recorded to ensure participant responses are accurately captured.

Final visit only:

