14. Biostatistics: We will use univariate analysis to summarize the measures of program usability and feasibility and examine their distributional properties (Aims 1 & 2). General/generalized mixed modeling analysis(41, 42) will be conducted for the primary and secondary effectiveness outcomes, to assess initial and sustained impacts of the adapted GLB intervention (Aim 3). More specifically, we will evaluate individual growth models for linear/nonlinear change from baseline to 6 months (level-1, time effects), overall group difference (level-2, group effect), and group difference in change (crosslevel, time-by-group interaction effect) (Hypothesis 3.1). Models will be adjusted for demographic variables (e.g. age, gender, ethnicity, disability severity, etc.), particularly if they are imbalanced after randomization, thereby providing more accurate estimates of the intervention impacts. We will also fit separate individual growth models for change from baseline to 12 months within both groups combined (time effects only) (Hypothesis 3.2). Our data will include missing observations due to either attrition or nonresponse. Intent-to-treat analysis will use restricted maximum likelihood estimation, which can produce unbiased estimates under the conditions of incomplete data. Subsequent intent-totreat analysis will utilize iterative Monte Carlo Markov Chain multiple imputation. (43) This approach includes all selected variables into the imputation process, which allows for greater recovery of the missing data.(44) All analyses will be performed using R(45) and SAS 9.3.(46) Secondary analyses will examine intervention effects for study completers who meet defined program adherence criteria.

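### Waist, upper arm circumference, BP, A1c and lipids have only two visits in the 0–6 month window, so the nonlinear and random-slope growth models are not identified; the version that can be fitted is valid but less precise than a baseline-adjusted comparison

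*Combined protocol and SAP*

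**What the plan says.** Section 14 (Biostatistics) states that mixed modelling "will be conducted for the primary and secondary effectiveness outcomes". For the controlled comparison it specifies "individual growth models for linear/nonlinear change from baseline to 6 months (level-1, time effects", an overall group effect, and "group difference in change (crosslevel, time-by-group interaction effect) (Hypothesis 3.1". Covariates are described thus: "Models will be adjusted for demographic variables (e.g. age, gender, ethnicity, disability severity, etc". On estimation: "Intent-to-treat analysis will use restricted maximum likelihood estimation", with multiple imputation as a later step. Section 14 does not fix a random-effects structure, give a separate model for outcomes with fewer visits, or name the baseline value of the outcome as a covariate.

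The visit schedule differs by outcome. Under Outcome measures in Section 3, primary outcomes "will be collected at baseline and again at 3, 6, and 12 months", while secondary outcomes "will be measured at baseline, 6, and 12 months and will include waist circumference, BP, A1c, serum lipids". Section 4 agrees: BP, upper arm circumference, waist circumference and the blood draw fall under the visit heading "Baseline, 6 months, and 12 months". The opening summary of Section 3 counts upper arm circumference among the secondary outcomes; the Outcome measures text treats it as a safety measure. Hypothesis 3.1 in Section 1 tests the secondary outcomes at 6 months.

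**The concern.** One model family is applied to two kinds of outcome. Weight and physical activity have three visits between baseline and 6 months, enough for a growth curve. The clinical secondary outcomes have two, which give each participant one change and no shape.

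Two things follow. First, part of what Section 14 allows (nonlinear change, person-specific slopes) has no content for these outcomes, and the plan does not say what replaces it. The choice among a change score, a baseline-adjusted comparison and a constrained-baseline model would then be made once data are in hand, and these give different estimates and standard errors. Second, the version that remains does not make full use of the baseline value already collected. The trial has 32 per group and is sized on the primary outcomes only, so precision on BP, A1c and lipids is worth keeping when it costs almost nothing.

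**Working it through.** **Inputs.** From the documents: 64 participants, 32 per group (Section 14); two visits, 0 and 6 months, for these outcomes in the controlled window (Sections 3 and 4). Assumed, because not given: two-sided alpha of 0.05; equal SDs at the two visits unless noted; correlation r between baseline and 6 months, shown as a range.

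**The plan's own figures.** Section 14 gives no figure on this point; its power statements cover weight and physical activity only. As a check on the working scale, the cited 6-month weight effect d = 0.91 with 32 per group gives power Φ(0.91 × √(32/2) − 1.96) = Φ(1.68), about 95%. This agrees with the stated 95% only if the 4% weight difference corresponds to d of about 0.91; no SD is stated. Nothing below depends on it.

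**Step 1: shape of change.** The design columns [1, t, t²] have rank 2 at visits 0 and 6, and rank 3 at visits 0, 3 and 6. A curve is estimable for weight, not for BP or A1c. (Section 11 mentions a 3-month albumin value that the Section 4 schedule lacks. Those passages need reconciling, but neither adds a 3-month value for the outcomes at issue.)

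**Step 2: person-specific slopes.** Let a be the intercept variance, b the slope variance, c their covariance and e the residual variance, with time coded 0 and 1. The observable elements are

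- variance at baseline: a + e
- covariance: a + c
- variance at 6 months: a + 2c + b + e

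That is three equations for four unknowns. Take variances 1.0 and 1.2 and covariance 0.7. Then e = 0.05 with (a, c, b) = (0.95, −0.25, 0.70) and e = 0.28 with (0.72, −0.02, 0.24) reproduce the same matrix exactly. Three visits give six elements, and all four parameters are identified. Fixing c at zero would bring the count to three, but the plan states no such restriction.

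**Step 3: what can be fitted.** A linear model with a random intercept (two variance parameters) or an unstructured covariance (three) is identified. In a simulated two-visit data set of 64 participants, the REML random-intercept fit converged with a time-by-group estimate of −0.3191 (SE 0.1754). The plain group difference in mean change was −0.3191 (SE 0.1754). The over-parameterised random-slope fit returned the same estimate and SE; only its variance components were arbitrary. Regressing the 6-month value on arm and baseline gave SE 0.1713.

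**Step 4: precision.** With n per group and common variance σ²:

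- change score: 2(1 − r) σ² × 2/n
- baseline-adjusted: (1 − r²) σ² × 2/n
- ratio: (1 − r²) / [2(1 − r)] = (1 + r)/2

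The detectable difference at 80% power, in SD units, is (1.96 + 0.84) × √(V × 2/32), with V = 2(1 − r) or 1 − r².

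| r | variance ratio | detectable difference, change score | detectable difference, adjusted |
|---|---|---|---|
| 0.5 | 0.75 | 0.70 | 0.61 |
| 0.7 | 0.85 | 0.54 | 0.50 |
| 0.8 | 0.90 | 0.44 | 0.42 |
| 0.9 | 0.95 | 0.313 | 0.305 |

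Sets of 3,000 simulated trials of 64 gave ratios of 0.76, 0.85 and 0.96 at r = 0.5, 0.7 and 0.9. Estimating the baseline coefficient costs a factor of about 1 + 1/(64 − 4) = 61/60. The gain is used up when (1 + r)/2 × 61/60 = 1, that is, at r = 120/61 − 1, about 0.97.

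With unequal SDs s0 and s1, the change-score variance minus the adjusted variance is (s0² + s1² − 2r·s0·s1) − s1²(1 − r²) = (s0 − r·s1)², which is never negative.

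**Step 5: do the planned covariates recover the loss?** Not as main effects. A person-level covariate adds the same amount at both visits and cancels from the change. In a separate simulated two-visit set of 64 complete cases, adding one left the time-by-group estimate identical and its SE at 0.2022. Adjusting for the baseline outcome value reduced the SE to 0.1787.

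**The case against.** The strongest reply is that Section 14 is not broken. It names a broad class of mixed models, allows linear as well as nonlinear change, and fixes no random-effects structure. A linear random-intercept model lies within its wording, fits two visits, and validly estimates the 6-month difference in mean change. This stands. A reader might infer that the secondary analyses cannot be run, will fail to converge or will be biased; the documents do not support that. Step 3 shows that even the over-parameterised fit left the treatment estimate and its SE intact, and Hypothesis 3.1 does not use the variance components.

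Second, the precision loss comes from leaving baseline means free, not from having two visits, so it is not peculiar to these outcomes. This is also right. The two-visit outcomes are where the plan needs a stated model in any case, so that is the natural place to choose the more efficient one.

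Third, r is unknown and the gain may be small: about 5% in variance at r = 0.9, and less above. That stands, and the result must be read as a range. Nor should the ratio be read as a shortfall in recruitment, because the sample size was set on the primary outcomes.

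Fourth, a simple 6-month regression drops participants without a 6-month value, whereas REML on repeated measures keeps their baseline data. Section 14 cites attrition of up to 23% at 6 months, or roughly 25 of 32 left per group (32 × 0.77 = 24.6). The remedy has to respect this.

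**Conclusion.** The point holds in a limited form. For waist circumference, upper arm circumference, BP, A1c and lipids, the nonlinear and the usual random-slope growth models are not identified between baseline and 6 months, and Section 14 states no reduced model. The version that can be fitted is valid but, with complete data, is an unadjusted change-score comparison. Baseline adjustment lowers the variance by 25% at r = 0.5, 15% at 0.7, 10% at 0.8 and 5% at 0.9, with essentially nothing gained above about 0.97.

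This rests on equal SDs at the two visits (the direction of the gain does not), all 64 participants contributing, and baseline values taken before allocation. Section 9 places consent at the baseline visit, which suggests that order without stating it.

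A reader might also infer that growth models should be dropped for these outcomes altogether. They should not: Hypothesis 3.2 runs to 12 months of intervention, where three visits (0, 6 and 12) are available. This is a cheap improvement in precision and clarity, not the repair of an invalid analysis.

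**What to change.** Add to Section 14, for Hypothesis 3.1 only: outcomes measured just at baseline and 6 months in the controlled window (waist circumference, upper arm circumference, BP, A1c and each lipid) are analysed by a REML mixed model with categorical time, unstructured covariance and baseline means constrained equal across arms; the treatment effect is the 6-month difference between arms. An essentially equivalent choice is the 6-month value regressed on arm and the participant's own baseline value, with the multiple imputation already planned applied to missing 6-month values. The mixed model is closer to the existing REML approach and keeps participants who have only a baseline value. Name one of the two as the analysis.

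Leave the Hypothesis 3.2 growth models for these outcomes in place.

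The cost is about one degree of freedom and a sentence or two of text. No new data or visits are needed.
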